### **II.C. Study Outcome Measures**

***Patient utilization of health services*** include 30-day ED visits, 30-day rehospitalizations

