### **II.D. Development and Validation of the Patient Survey Instruments**

Westat will develop a draft survey instruments consisting of items designed to elicit patient experiences with the delivery and receipt of TC components, as well as patient-reported outcomes relevant to transitions in care.

Draft items will be derived from TC measurement constructs identified from an updated literature review, existing validated instruments such as the Coleman CAHPS Care Transition questions, items listed in the NIH PROMIS repository, and constructs elicited from focus groups and hospital site visits. Draft instruments will be refined based on at least two cycles of iterative review by members of the ACHIEVE study team, including members with relevant clinical expertise, TC program development and implementation expertise, and patient and caregiver experience.

Once draft items have been developed, cognitive interviews will be conducted to examine item clarity, comprehension, difficulty, and face validity. Cognitive interviews will be conducted with up to 14 participants in two iterative rounds. The patient survey will also be translated into Spanish and up to 6 cognitive interviews will be conducted to pretest the translated items. The surveys will be revised as needed based on feedback from the cognitive interviews, in preparation for pilot testing.

Significant changes were required in the administration of the patient and caregiver survey component of Project ACHIEVE based on uncovering potential conflict with CMS HCAHPS. Numerous follow-up conversations with CMS, HSAG, PCORI and the ACHIEVE research team yielded agreement on Project ACHIEVE being allowed to field its patient survey 51 days after patient hospital discharge; after most patients contacted for HCAHPS have completed their survey and without causing significant disruption to hospitals' participation in HCAHPS. Of note, we originally proposed to call patients between 30 and 45 days post discharge.

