Using the data from the survey pilot, item analysis and internal consistency reliability tests will be conducted to determine if there are items that should be dropped and/or to identify items that are not operating as expected. Item analysis will consist of examining item frequencies and missing percentages to ensure that there is item variability and low levels of missing data when the item should have been answered. High levels of missing data may signal either an issue with the way the item is worded or an inappropriate topic for the population. On the patient and caregiver surveys, telephone interviewer comments will also be considered to determine if certain items were problematic or unclear for respondents. Internal consistency reliability tests will be conducted on the a priori theoretical constructs of interest within the survey using a threshold of a Cronbach's alpha of at least 0.70 to be considered acceptable. Item grouping and inclusion will be refined based on the small-scale pilot validation results in order to improve reliability and validity of item scales.

After completion of survey validation work from the pilot tests, the survey instruments will be revised prior to the main survey data collection.

The ACHIEVE survey pilot study was conducted from December 6 2016 to April 30, 2017, with **132** completed patient surveys, **38%** overall response rate (42% mail with phone follow up; 30% phone only).

The pilot survey response rates were lower than estimated in original proposal. Literature demonstrates that a multi-wave, mail survey with telephone follow-up yields a better response rate than a phone-only protocol. Further, the addition of an incentive, whether promised or pre-paid, will also improve response rates, compared to a design without any incentive. Of note, we are unable to promise an incentive to hospitalized patients when they are approached about Project ACHIEVE per guidance from CMS. Proposed changes to the data collection protocol for patients:

1. Initial survey packet mailed to all patients, including \$5 cash incentive payment in the envelope

2. Thank You reminder post card (mailed to all)
3. 2nd survey packet mailed to those who do not respond to the first survey
4. Telephone follow-up with those who do not respond to either mail survey

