#### **II.F. Analysis of Patient Survey Datasets**

**Psychometric analysis.** Westat will compile patient survey data from the main study, conduct data cleaning, and generate descriptive statistics from the survey results. Psychometric analyses will be conducted to examine items for variability of response, missing percentages, calculate reliability statistics, perform confirmatory factor analysis to examine the factor structure of the measures, and examine inter-correlations of items and composites. Final composite scores will be created and the survey data will then be used to examine the study's aims and hypotheses regarding TC delivery and outcomes.

**Descriptive statistics.** Continuous variables will be summarized with descriptive statistics (n, mean, standard deviation, median, quintiles, and min and max); categorical variables will be described with counts and percentages. All data will be unweighted. For each survey type

(i.e., patient, caregiver, provider), numerical and/or graphical summaries will be provided overall and by subpopulations.

**II.G. Analysis of TC Component Exposure.** Analyses will be conducted using both hospital- and patient/caregiver-level data. Comparisons on outcomes will be made first using TCCs identified by the hospital; additional analyses will use patient/caregiver identified components. Moreover, additional analyses will also use the number and occurrence of specific categories received within a component as a measure of the TCC received. Finally, an additional issue for consideration is that indicators for TCC presence or absence may not be sufficient for identifying TC component “exposure.” It is expected that TCCs in different communities/hospitals will be implemented to varying degrees. Non-uniform implementation may provide a natural experiment where communities/hospitals serve as their own control and the longitudinal effects of the TC component can be investigated. Using process and implementation data collected at Phase 2, segmented regression analysis of interrupted time series data will allow for comparisons and the estimation of effects for different intensities of TC component exposure.

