Although every effort will be made to include the possible combinations of TC components, it is unlikely that all combinations will be present in each subpopulation. Additionally, although many TC component factors will be measured, it is not expected that all of them will impact the outcomes (sparsity of effects). As an alternative to the factorial design utilized in an experiment, fractional factorials may also be utilized, where a large number of factors can be “screened” to detect important factors even in the presence of a small number of hospitals.

As an additional visualization tool, tree-based models (CART and Random Forests) may also be used to identify potential higher-order interactions. Although the primary analysis will be conducted within a subpopulation, exploratory analyses will be used to investigate the interaction of subpopulation characteristics, patient/caregiver characteristics, and TC components on outcomes. The identification of these potential combinations will help inform additional comparative analyses in the presence of a large number of potentially correlated variables.

- **Pooled Analysis**

Based on the statistical power available with a survey response rate of 35 percent, we conclude that the resulting sample size of approximately 9000 patients from 46 hospitals represents the minimum sample required to ensure that the ACHIEVE prospective analysis can detect the comparative effects of transitional care strategies on important patient outcomes of interest. Our power analysis is based on the study’s ability to detect meaningful differences in outcomes across groups of hospitals that implement different combinations of transitional care (TC) components. Results from the ACHIEVE survey pilot test indicate that the patient survey response rate could be as low as 35 percent. To assess the impact of this response rate on statistical power, we conducted a Monte Carlo simulation using data from the ACHIEVE retrospective analysis, which includes Medicare claims data from nearly 400 hospitals and all Medicare patients hospitalized at these facilities

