## Flow Chart of Patient Records in Project ACHIEVE Analytic File

## Flow Chart of Patient Records in Project ACHIEVE Analytic File

## Flow Chart of Patient Records in Project ACHIEVE Analytic File

a HIC/MBI—Health Insurance Claims/Medicare Beneficiary Identification Number. This was required to be able to link patient responses to their health care utilization data.

b Clinical Classification System (CCS). CMS methodology requires mapping certain diagnosis codes to CMS diagnosis coding system. If the patient's diagnosis code was unable to be mapped, the record was excluded.

c Other reasons for exclusion include ineligible diagnosis codes (e.g., rehab = 274, cancer = 101, psychiatric = 13, discharged against medical advice, AMA = 19, transfer = 71).

dATA = Applicable to All questions. To ensure higher quality data, we determined that 50% of all questions that were applicable to all participants must be complete for a record to be included in the final dataset.

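### The comparison made first needs no survey answer, yet appears limited to day-51 survey respondents, with no named method for response that depends on the outcome

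*Combined protocol and SAP*

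**What the plan says.** - **Exposure.** Section II.G (Analysis of TC Component Exposure): "Comparisons on outcomes will be made first using TCCs identified by the hospital". Components reported by patients and caregivers enter in additional analyses.
- **Outcome.** Section II.C: the utilisation measures "include 30-day ED visits, 30-day rehospitalizations".
- **Sample.** The Pooled Analysis text states that "the resulting sample size of approximately 9000 patients from 46 hospitals represents the minimum sample required". Its simulation takes 560 recruits from each of 46 hospitals and keeps a random 35% of them. It groups hospitals into five TC clusters and compares 30-day readmission in a logistic model with patient covariates. The stated detectable difference is 2.1 to 2.9 percentage points.
- **Dataset.** The flow-chart notes say of the Medicare identifier: "This was required to be able to link patient responses to their health care utilization data". They also say that "50% of all questions that were applicable to all participants must be complete for a record to be included" in the final dataset.
- **Timing and fielding.** Section II.D: the project may "field its patient survey 51 days after patient hospital discharge". Patients get up to two mailed packets with a prepaid incentive in the first, a reminder card, and then "Telephone follow-up with those who do not respond to either mail survey".
- **Nonresponse.** Section II.E will examine refusals and nonresponse by patient and hospital subgroup and correct where it can. It gives no method. Under Descriptive statistics: "All data will be unweighted". The Inferential Analysis paragraph names GEEs and GLMMs with hospital, patient and community characteristics, and no weights or selection model.

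**The concern.** The exposure in this comparison comes from the hospital, and 30-day utilisation can be read from claims. A survey answer is needed for neither. If the comparison is nevertheless run only in respondents, roughly two thirds of recruits are dropped for a reason unrelated to what is being measured.

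The timing makes this more than a loss of precision. The survey is fielded 21 days after the 30-day window closes (51 − 30), so a patient's readmission, or the illness behind it, can influence whether that patient answers. Selection into the analysis may then depend on the outcome. The power simulation draws respondents at random, so it allows for fewer patients but not for selection of this kind. Covariate adjustment removes response differences explained by the measured covariates. It does not remove dependence on the outcome itself. Respondent data alone cannot reveal that dependence.

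**Working it through.** **1. The plan's own sample figure.** Inputs from the simulation description: 46 hospitals, 28 weeks, 20 patients per week, 35% response.

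- Recruits: 46 × 28 × 20 = 46 × 560 = 25,760.
- Respondents: 25,760 × 0.35 = 9,016, which reproduces the stated figure of about 9,000.
- Left out: 25,760 − 9,016 = 16,744.

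Starting from 9,000 completes and the plan's own response rates:

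| Response | Source | Implied recruits | Non-respondents |
|---|---|---|---|
| 35% | assumed minimum | 25,714 | 16,714 |
| 38% | pilot, overall | 23,684 | 14,684 |
| 42% | pilot, mail with phone | 21,429 | 12,429 |
| 45% | pre-launch projection | 20,000 | 11,000 |

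These are rough upper figures for what could be added back. Section II.D reports reduced recruitment. The response-rate formula in II.E counts partial completes and handles unknown eligibility. The identifier, diagnosis and other exclusions in the flow-chart notes are not deducted.

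**2. How outcome-dependent response acts.** Let p be the true readmission risk, r1 and r0 the response rates of readmitted and other patients, and k = r1/r0. Among respondents:

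- observed risk = p·r1 / (p·r1 + (1 − p)·r0)
- observed odds = k × true odds
- for clusters A and B, unadjusted: observed OR = true OR × (kA/kB)

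A common k leaves the unadjusted odds ratio unchanged and creates no false difference. It does compress a true difference in points: with k = 0.8 everywhere and the higher-risk cluster at 15% to 20%, a true 2.9 points appears as about 2.5.

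**3. Illustrations.** There is no true difference. The 18% risk and every response split are assumptions; the documents give none of them.

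- Cluster B, 30% v 36% (readmitted v others): 0.054 / (0.054 + 0.2952) = 15.46%.
- Cluster A, 25% v 37%: 0.045 / (0.045 + 0.3034) = 12.92%. The false difference from B is 2.55 points; OR (B v A) = (0.30/0.36)/(0.25/0.37) = 1.23.
- Cluster A, 28% v 36.4%: 0.0504 / (0.0504 + 0.29848) = 14.45%. The false difference is 1.02 points, OR 1.08, below the detectable range.

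In the first pair the overall response rates are 34.9% (0.054 + 0.2952) and 34.8% (0.045 + 0.3034). Comparing overall response by cluster would not show the problem.

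**4. Tipping ratio.** Reference cluster kB = 0.30/0.36 = 0.833, p = 0.18, observed 15.46%.

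- A false 2.1 points needs an observed 13.36% in A, so kA = 0.703 and kA/kB = 0.843.
- A false 2.9 points needs 12.56%, so kA = 0.655 and kA/kB = 0.786.
- For assumed risks of 15% to 20%, the ratios run from 0.817 to 0.856 for 2.1 points and from 0.749 to 0.804 for 2.9 points.

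Ratios closer to 1 stay below the detectable range.

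**5. Precision gained from using all recruits.** The ratio of detectable differences is √{[(1 + (n2 − 1)·ICC)/n2] / [(1 + (n1 − 1)·ICC)/n1]}, with n1 = 9,000/46 = 195.7 per hospital. The ICCs are assumed.

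| ICC | n2 = 559.0 (35% response) | n2 = 434.8 (45% response) |
|---|---|---|
| 0.005 | 0.82 | 0.85 |
| 0.01 | 0.88 | 0.90 |
| 0.02 | 0.93 | 0.94 |

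**The case against.** **The restriction is inferred.** The sample-size sentence sets a completion target, the 35% draw is a power-simulation step, and the 50% rule is a past-tense flow-chart note. The notes alone do not show whether another file served the hospital-level models. A reader might infer that the plan expressly limits this comparison to respondents; no sentence does. This objection stands. What remains is that the population is unstated and the available signs point one way.

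**First is not primary.** Section II.G gives an order, warns that presence or absence of a component may be an inadequate measure of exposure, and places the primary analysis within subpopulations. This part of the study exists to collect patient-reported detail, for which respondents are the natural population. This stands too, and the point is confined to the hospital-level models.

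**The hospital-level question is covered elsewhere.** The retrospective analysis uses claims for all Medicare patients at nearly 400 hospitals, with no survey step. This stands in part. It covers an earlier period (the power data are from 2013-14), the documents do not say whether its hospitals overlap the 46, and it cannot test selection in this sample.

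**Nonresponse is not ignored.** Section II.E commits to examining it, the same multi-wave fielding is proposed for all patients, and the models adjust for covariates. True, but no correction is named, and the check is by subgroup and not by outcome. A reader might take the unweighted-data sentence as ruling out weights in the outcome models. It sits under Descriptive statistics and does not do that.

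**The bias is hypothetical, and the remedy may be unavailable.** Both are fair. No passage shows a response gap that differs between clusters, and linkage of non-respondents is unconfirmed.

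**Conclusion.** The point holds as a low-cost improvement. The plan does not state the population for its hospital-level models, appears to use respondents only (about 9,000 of up to 25,760 planned recruits), and has no committed method for response that depends on a 30-day outcome already fixed when the survey goes out.

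The tempting stronger conclusion is that the first comparison is biased by some 2 to 3 points. The documents do not support it. A false difference needs outcome-dependent response that differs between clusters, which they neither show nor exclude. The 18% risk, the response splits and the ICCs are illustrations and not evidence of size. Under them, the smallest detectable difference is mimicked only if kA/kB falls to about 0.82 to 0.86, and one of the two worked contrasts stays below the detectable range. The odds-ratio relation is exact for an unadjusted contrast and approximate for the planned adjusted GEE and GLMM.

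**What to change.** 1. **State the population** for the hospital-level models.
2. **Add a supporting analysis where authorisation and identifiers permit.** Analyse hospital-level exposure and 30-day utilisation in all authorised, linkable patients who remain after the diagnosis and other eligibility exclusions. Drop the survey-response and 50%-item conditions, and report the result beside the respondent analysis.
3. **Name the correction.** For models that need survey-reported exposure, or if non-respondents cannot be linked, replace the open-ended promise in II.E with pre-specified inverse-probability-of-response weights. Build them from hospital and discharge-list variables, adding claims variables including the outcome where available. State that weights without the outcome do not remove outcome-dependent selection.
4. **Label any tipping-point analysis.** If observed OR = true OR × (kA/kB) is used, report the ratio at which the conclusion changes and say that it is exact only for unadjusted contrasts.

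**Cost.** Extra linkage and analysis work, with no new patient contact. Step 2 depends on authorisation scope, which the documents do not show. Section II.D expected authorisation to be obtained from 27,000 patients, but the identifier note speaks only of linking responses. Main survey administration began in June 2017, so authorisations signed before this December 2017 version cannot be reworded. If linkage is barred, only steps 1, 3 and 4 apply, and for outcome-dependent response step 4 rests on assumed inputs. Selection at approach and authorisation remains in every case.

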Before the main survey administration, using pilot survey estimates, we expected to approach and obtain HIPAA authorization from 27,000 patients (45 participating hospitals approaching an estimated average of 20 patients per hospital per week during the 30-week recruitment period), and have 12,150 completed patient survey (a 45% response rate). Since launching the main survey administration in June 2017, several factors have conspired to reduce the expected patient and caregiver recruitment from participating hospitals. Therefore, we propose to reduce the target number of completed patient surveys from 12,000 to 9,000 and extended the recruitment end date from Jan 21, 2018 to April 15, 2018 for adequate sample size to detect the comparative effects of transitional care strategies on important patient outcomes of interest.

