#### **II.E. Response Rates, Missing Values and Data Imputation on the Survey Data Collection Datasets**

Response rates for the main data collection will be calculated using AAPOR response rate formula 4 (RR4). This formula includes both complete and partial completed surveys/interviews for inclusion in the numerator and allocates cases of unknown eligibility in the denominator. This is particularly important given that the phone number data may be incomplete, incorrect, or phone numbers may be disconnected and we therefore may not be able to know the eligibility of the case. We will examine survey refusals and nonresponse to determine if there is the potential for nonresponse bias based on certain patient subgroups and/or hospital subgroups and make corrections if possible.

For item nonresponse, we will examine if certain items have higher missing data than others. Given that the patient surveys will be designed to assess experiences with care, if the respondent does not indicate that they experienced a specific care component, we will not impute data on their experience with it.

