over five years. This simulation allowed us to assess the likely statistical power of the prospective analysis even though we do not yet know with certainty the distribution of TC components and patients across participating hospitals. This simulation assumes that the distribution of TC components and patients among hospitals recruited for the ACHIEVE prospective study will be consistent with the distributions observed in the larger population of hospitals included in the ACHIEVE retrospective study.

We conducted the simulation as follows: (1) we drew a random sample of 46 hospitals from the nearly 400 hospitals included in the ACHIEVE retrospective data; (2) we drew a random sample of 560 patients from each of the 46 selected hospitals, corresponding with the planned data collection period of 28 weeks and the planned recruitment rate of 20 patients per week at each facility; (3) we drew a random sample of 35 percent of the recruited patients at each hospital, corresponding with the assumed minimum response rate; (4) we used the 5 clusters of TC components identified from the ACHIEVE retrospective analysis to classify hospitals into comparison groups based on which TC components they implemented for their patients; and (5) we used a multivariable logistic regression model to estimate minimum detectable differences (using a 5% significance level) in 30-day all-cause readmission rates across hospitals grouped by TC clusters, while controlling for patient characteristics that may impact readmission (e.g., age, race, sex, comorbidities, and dual eligible status, as well as others), and accounting for patient clustering within hospitals. We used 1000 replications of this simulation to estimate the variances in minimum detectable differences.

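### The 9,000 figure serves as both the completed-survey target and the minimum analysed sample, with no allowance for records that the analytic file leaves out

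*Combined protocol and SAP*

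**What the plan says.** Section II.D (Development and Validation of the Patient Survey Instruments) reports that recruitment fell behind after the main survey began, and proposes to "reduce the target number of completed patient surveys from 12,000 to 9,000". There the 9,000 counts surveys completed.

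The Pooled Analysis text in II.G states that a "sample size of approximately 9000 patients from 46 hospitals represents the minimum sample required". The number comes from a simulation on the retrospective Medicare claims data: "we drew a random sample of 46 hospitals from the nearly 400 hospitals", then 560 patients per hospital, then 35% of those as respondents. All simulated respondents enter a logistic model for 30-day readmission. The result is a minimum detectable difference (MDD) of 2.1 to 2.9 percentage points. On that basis 35% is called the minimum acceptable response rate. Here the 9,000 counts patients analysed.

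The footnotes to the Flow Chart of Patient Records describe what a record needed in order to be in the analytic file:

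- A Medicare identifier (HIC/MBI): "This was required to be able to link patient responses to their health care utilization data".
- A diagnosis code that could be mapped to the CMS system.
- No ineligible diagnosis or discharge type. The examples given are "rehab = 274, cancer = 101, psychiatric = 13", followed by 19 discharges against medical advice and 71 transfers.
- Enough of the questionnaire answered: "50% of all questions that were applicable to all participants must be complete for a record to be included in the final dataset".

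Section II.E adds that the response-rate formula for the main data collection "includes both complete and partial completed surveys/interviews for inclusion in the numerator".

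**The concern.** One number does two jobs. A completed survey becomes an analysed record only after it has been linked to claims, passed the diagnosis rules and passed the completeness rule. The simulation has a single attrition step, non-response. It cannot reflect linkage loss, because its patients were drawn from claims, where the utilization outcome is present by construction. Since partial surveys count as responses in II.E, some of the main survey's respondents may also fail the 50% completeness rule.

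Two things are at stake. A study that collects its 9,000 surveys and stops would hold fewer analysable records than the plan calls the minimum. And the 2.1 to 2.9 point MDD, which is the ground for accepting a 35% response rate, would describe a somewhat larger file than the one analysed.

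**Working it through.** **Inputs from the documents.** 46 hospitals, 560 recruits per hospital (28 weeks × 20 per week), 35% response, MDD of 2.1 to 2.9 points and a reference effect of 3.6 points (all Pooled Analysis, II.G); target of 9,000 completes (II.D); pilot response of 38% overall and 42% for mail with phone follow-up (II.D).

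**Inputs assumed.** The total loss d between completed survey and analysed record is not visible, so 5%, 10%, 20% and 30% are used. The intracluster correlation (ICC) is not given, so 0.01 is used, with 0 as the limiting case.

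**Step 1: reproduce the plan's figure.** 46 × 560 = 25,760 recruits, and 25,760 × 0.35 = 9,016 respondents, or 196 per hospital. This agrees with the stated figure of about 9,000, so the plan's multiplication is correct. The MDD itself cannot be reproduced, because the power, baseline rate and ICC are not stated.

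**Step 2: slack.** 9,016 − 9,000 = 16 records, and 16 / 9,016 = 0.18%.

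**Step 3: records left and effect on the MDD.** Analysable N = 9,016 × (1 − d). With m = 196 and m₂ = 196 × (1 − d), the MDD is multiplied by

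√{ [(1 + (m₂ − 1) × ICC) / m₂] ÷ [(1 + (m − 1) × ICC) / m] },

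which reduces to √[1 / (1 − d)] when ICC = 0.

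| Assumed loss | Analysable N | MDD increase, ICC 0.01 | MDD increase, no clustering |
|---|---|---|---|
| 5% | 8,565 | 1% | 3% |
| 10% | 8,114 | 2% | 5% |
| 20% | 7,213 | 4% | 12% |
| 30% | 6,311 | 7% | 20% |

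Worked case, 30% loss at ICC 0.01: m₂ = 137.2. The new variance term is (1 + 1.362) / 137.2 = 0.01722 and the old one is (1 + 1.95) / 196 = 0.01505. The square root of their ratio is 1.0695. Then 2.1 × 1.0695 = 2.2 and 2.9 × 1.0695 = 3.1. Without clustering the factor is √(1 / 0.7) = 1.195, giving 2.5 and 3.5.

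**Step 4: loss needed to matter against the plan's reference.** Without clustering, 2.9 rises to 3.6 when d = 1 − (2.9 / 3.6)² = 35%. With clustering a larger loss would be needed.

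**Step 5: headroom if response exceeds 35%.** 25,760 × 0.38 = 9,789, which could lose 1 − 9,000 / 9,789 = 8% before falling below 9,000. 25,760 × 0.42 = 10,819, which could lose 17%.

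**The case against.** The strongest reply is that no shortfall has been shown. The flow-chart boxes are not visible, so neither the starting number, the final number nor the total loss is known. The footnotes are in the past tense and report how a file was built; the diagnosis and completeness rules may have been settled after the simulation was run. A target is not a cap, and 35% was chosen as a floor. The pilot did better, the mail-plus-phone mode was then proposed for all patients with a prepaid incentive, and step 5 shows that this could absorb a moderate loss. The plan also says approximately 9,000, so a handful of records would not matter.

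Much of this stands, and it limits the size of the point. It does not remove it. The linkage need follows from the outcomes in II.C (30-day ED visits and rehospitalizations), whenever the other rules were set. The plan nowhere offers the gap between 35% and the pilot rates as an allowance for exclusions, and II.D says that recruitment was running below expectation. The combined document now holds the target, the minimum and the exclusions without reconciling them.

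Three stronger readings are tempting, and the documents do not support them:

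- **That the final file fell to about 8,522.** The listed exclusions add up to 274 + 101 + 13 + 19 + 71 = 478, and 9,000 − 478 = 8,522. But the figures are only presumed to be record counts, they are given as examples, and the stage at which those records left is not shown.
- **That the response-rate formula itself inflates the 35%.** II.E says only that partial surveys enter the numerator and that cases of unknown eligibility are allocated in the denominator. The 35% is drawn from the pilot and is not described as a rate on that formula.
- **That the pooled analysis is underpowered.** Steps 3 and 4 show a modest effect, with the MDD below 3.6 points throughout the assumed range.

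**Conclusion.** The point holds as a minor one. The plan uses about 9,000 both for completed surveys and for the minimum number analysed for readmission, and makes no allowance for the linkage, diagnosis and completeness exclusions. Any loss above about 0.2% puts a study that just meets its target below its stated minimum, and makes the 2.1 to 2.9 point MDD slightly optimistic for the analysed file.

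The actual loss cannot be established from the documents; the sizes in the table rest on the assumed losses. The ICC of 0.01 is also assumed. Because the planned model accounts for clustering within a fixed 46 hospitals, the no-clustering column is an upper bound and not a description of the planned analysis. A response rate above 35% could offset some of the loss, but the plan does not say so.

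**What to change.** Add an analysable fraction to step (3) of the simulation: the share of respondents who can be linked, have a mappable and eligible diagnosis, and have answered at least 50% of the applicable-to-all items. Take it from the pilot or from the records collected to date. Restate N and the MDD on analysable records. In II.D and in the Pooled Analysis text of II.G, label 9,000 as completed surveys and give the expected analysable number beside it. If response above 35% is relied on to cover the exclusions, say so and show the figure.

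The cost is one extra simulation input, a rerun, and a slightly less favourable stated MDD. No extra enrolment is proposed.
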